3 STUDY DESIGN

3.1 STUDY DESIGN OVERVIEW

Subjects who have completed the AP-003-C main study (n=161) will be offered the option to roll-over to the open label extension study (AP-003-C-OLE) at their final visit of the AP-003-C main study (Visit 7). Enrollment into the AP-003-C-OLE study (Visit 9) allows a 170-day screening window from the AP-003-C main study Visit 7. AP-003-C-OLE study will include the following visits:

Visit 9/Enrollment (Day-170 to Day 0, but not to occur before completion of AP-003-C main study) in-office visit, Visit 10 (24 hours after enrollment post injection follow-up telephone call), Visit 11 in-office visit (Day 84 ±14 days), Visit 12 (24 hours after Visit 11 post injection follow-up telephone call), Visit 13 in-office visit (Day 168 ± 14 days), Visit 14 (24 hours after Visit 13 post injection follow-up telephone call), Visit 15 in-office visit (Day 252 ± 14 days), Visit 16 (24 hours after visit 15 post injection follow-up telephone call), Visit 17 final in-office visit (Day 280 ± 14 days).

The safety of repeat dosing will be evaluated at all visits; in-office visit safety assessments will include vital signs, physical exams, evaluation of AEs, and laboratory analysis. Phone visits will evaluate for AEs.

The clinical effects of treatment on OA pain will be evaluated during all in-clinic visits using the Western Ontario and McMaster Universities Arthritis Index (WOMAC®) osteoarthritis Index 3.1 and the Patient's Global Assessment of disease severity (PGA). The WOMAC will also be utilized to assess the contralateral knee pain at Enrollment/Visit 9 and Visit 17 (or Early Termination Visit).

The WOMAC® is a validated pain scoring system and sets the standard for the subject response. In order not to bias the collection of data, only questions from the validated WOMAC pain scale will be asked of subjects.

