9.3 RECORDING OF ADVERSE EVENTS AND SERIOUS ADVERSE EVENTS

Recording and reporting of adverse events should be in accordance with the FDA final “Guidance for Industry and Investigators Safety Reporting Requirements for INDs and BA/BE Studies” of December 2012.

Any AE is to be recorded in the eCRF. In order to avoid vague, ambiguous, or colloquial expressions, the AE should be recorded in standard medical terminology rather than the subject’s own words. Whenever possible, the investigator should combine signs and symptoms that constitute a single diagnosis.

The existence of an AE may be concluded from a spontaneous report of the subject; from the physical examination; or from special tests e.g., laboratory assessments, where applicable, or other study-specified tests (source of AE).

The reporting period begins from the time that the subject receives their first IA injection at the Baseline visit of the AP-003-C main study through subject’s Final Visit 17 at 40 weeks of AP-003-C-OLE study. Any events continuing at study exit will be followed for 30 days or to resolution, or until no improvement is expected, whichever comes first. Any SAE occurring after the reporting period must be promptly reported if a causal relationship to the investigational drug is suspected. If the subject begins a new therapy, the safety reporting period ends at the time the new treatment is started, however, death must always be reported when it occurs during the study period irrespective of intervening treatment.

Each AE is to be evaluated for duration, severity, seriousness, and causal relationship to the investigational drug. The action taken and the outcome must also be recorded.

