10.3.7 Number of subjects to receive study drug

Planned enrollment is up to 161 subjects; all subjects that consent to participate in the AP-003-C-OLE study. Assuming a 15% dropout rate, a total of 136 subjects will be enrolled.

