10.4 STUDY ENDPOINTS

10.4.1 Primary Endpoint

- Incidence and severity of treatment-emergent adverse events (TEAEs).

These incidents will be summarized by number and percent of subjects having an event, the number of events per subject, and frequency of events in study population.

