3. PRIMARY STUDY ENDPOINTS

3.1 Primary Endpoint

The primary trial endpoint is to evaluate the incidence and severity of treatment-emergent adverse events (TEAEs)

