4. HYPOTHESES AND METHODS

4.1 Primary Analysis Methodologies

Since this is an observational study on the repeat administration of Ampion 4 mL injection, no formal hypotheses will be tested in this study. There will be no comparisons made to threshold values or to “historical” control values. There is no comparator in this study.

All analyses will be descriptive in nature and will be performed at each efficacy assessment (Visit 9 (Enrollment), Visit 11 (Week 12), Visit 13 (Week 24), Visit 15 (Week 36) and Visit 17 (Week 40)). For dichotomous outcomes, the percentage of patients with that outcome will be estimated and exact 95% binomial confidence intervals will be calculated. These dichotomous outcomes are:

- The incidence of treatment emergent adverse events
- Responder status based on the OMERACT-OARSI responder criteria
- Evaluate OMERACT-OARSI ‘controlled’ responder defined as a 20% improvement in Pain and Function and 0.5 point absolute change in the 5-point Likert Scale
- Evaluate 20% improvement in PGA and 0.5 point absolute change in the 5-point Likert Scale

The outcomes with more continuous responses will be analyzed via descriptive statistics (n, mean, standard deviation, median, minimum, and maximum). Also, 95% confidence intervals from the mean response will be calculated. These outcomes are:

- Mean change and percent change in WOMAC A pain subscore
- Mean change and percent change in WOMAC B stiffness subscore
- Mean change and percent change in WOMAC C physical function subscore
- Mean change and percent change in PGA
- Mean Change and percent change in WOMAC A pain subscore questions 1 and 2 (pain with movement)
- Mean Change and percent change in WOMAC A pain subscore questions 3–5 (resting pain)
- Change in contralateral knee pain (WOMAC A)
- Change in contralateral knee stiffness (WOMAC B)
- Change in contralateral knee function (WOMAC C)

Differences in pain scores between successive visits will be estimated via descriptive statistics and confidence intervals.

The time to total knee replacement will be summarized using Kaplan-Meier methodologies. The use of rescue analgesia will be summarized as the dichotomous outcome on the number of patients using rescue medication and as continuous variables on the number of medications use.

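### The primary TEAE percentage takes no account of unequal exposure and has no single observation window, so it does not estimate risk over 52 weeks or over five injections

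*SAP*

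**What the plan says.** The primary endpoint is the incidence and severity of TEAEs (Protocol 3.5.1, SAP 3.1). SAP 4.1 puts TEAE incidence first among the dichotomous outcomes and gives the estimator: "For dichotomous outcomes, the percentage of patients with that outcome will be estimated and exact 95% binomial confidence intervals will be calculated". Protocol 10.4.1 says "These incidents will be summarized by number and percent of subjects having an event", together with "the number of events per subject, and frequency of events in study population". Protocol 10.4.2 adds tabulations by body system, preferred term, seriousness, severity and relationship.

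None of these has a time or injection denominator, and tables 14.3.1 to 14.3.10.4 in SAP Section 7 contain none either. The one method that handles censoring is reserved for an exploratory endpoint: "The time to total knee replacement will be summarized using Kaplan-Meier methodologies".

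The denominator is everyone enrolled in the extension with at least one dose (Protocol 10.3.1). The objective is safety with dosing every 12 weeks for 52 weeks and/or five injections in total (Protocol 3.2.1, SAP 2.1).

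On timing, Protocol 9.3 states: "The reporting period begins from the time that the subject receives their first IA injection at the Baseline visit of the AP-003-C main study". Protocol 3.1 states: "Enrollment into the AP-003-C-OLE study (Visit 9) allows a 170-day screening window from the AP-003-C main study Visit 7".

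**The concern.** A percentage of subjects with an event can be read as a risk over a period only if subjects are observed for about the same time, or if shorter follow-up is handled in the analysis. Here neither is assured, for three reasons.

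- **Early leaving.** A subject who takes one extension dose and leaves without an event counts the same as an event-free completer.
- **Early end of reporting.** Under Protocol 9.3 the safety reporting period closes when a new therapy starts, apart from deaths.
- **Unequal numbers of Ampion injections.** The main study was randomised 6:1 (Protocol 1.2) and included saline subjects (SAP 2.4). The extension gives injections at Visits 9, 11, 13 and 15 (Protocol 5), so a former saline subject can reach four Ampion injections but not five.

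In addition, the window is not fixed, so two analysts following the documents could count different events over different lengths of time. What is at stake is whether the trial's main safety figure can be related to a year of treatment, to five injections, or to results from other studies.

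**Working it through.** **1. The plan's own figure.** Protocol 10.3.7 says "Planned enrollment is up to 161 subjects" and gives 136 after 15% dropout. 161 × (1 − 0.15) = 136.85, which truncates to 136, so the figure is reproduced. The documents give no expected TEAE rate and no precision for the primary endpoint, so there is nothing further to reproduce.

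**2. The windows, side by side.**

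| Place | Start or end of observation |
|---|---|
| Protocol 9.3, 10.3.6 | AE reporting and time on study start at the first main-study dose; AE reporting runs to Visit 17 |
| SAP 4.2 | Time on study starts at the initial dose of this study |
| SAP 5.2 | A TEAE starts or worsens after an initial dose; which study is not stated |
| SAP 4.7.4 | AE follow-up ends 12 weeks after first dose, yet AEs are documented through end of study |

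**3. Completer observation time** (Visit 7 taken as Day 84, Visit 17 as Day 280 ± 14).
- Extension clock: 280 − 14 = 266 to 280 + 14 = 294 days; ratio 294/266 = 1.11.
- Main-study clock: 84 + 0 + 266 = 350 to 84 + 170 + 294 = 548 days; ratio 548/350 = 1.57.
- 12-week limit in SAP 4.7.4: 84 days for every completer.

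**4. Ampion injections.** Main-study Ampion subjects: 1 + 4 = 5. Former saline subjects: 0 + 4 = 4. If the arms roll over in the 6:1 proportion (an assumption), about 161/7 = 23 subjects cannot reach five.

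**5. Size and direction (illustration).** Assumptions:
- Constant hazard λ = −ln(1 − p)/w and risk R(t) = 1 − exp(−λt), with t in weeks.
- p from Protocol Table 1.5.4: 421/932 for any TEAE, 73/932 for related TEAE.
- w = 12 or 20 weeks. That table pools six studies, including two with Week 20 endpoints, so its follow-up length is not known.
- A fraction d = 0.15 leaves, uniformly over the 40 extension weeks.

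Extension clock: crude = 0.85 × R(40) + 0.15 × mean of R(u), u uniform on 0 to 40. For any TEAE with w = 12: λ = 0.0501 per week, R(40) = 0.865, mean R(u) = 0.568, so crude = 0.85 × 0.865 + 0.15 × 0.568 = 0.821.

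Main-study clock: the same, with 12 weeks plus a gap g added to each subject's time, g uniform on 0 to 170 days, compared with R(52).

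| Outcome, w | Extension clock: crude vs R(40) | Main-study clock with gap: crude vs R(52) |
|---|---|---|
| Any, 12 | 82.1% vs 86.5% (−4.5) | 94.3% vs 92.6% (+1.7) |
| Any, 20 | 65.7% vs 69.9% (−4.2) | 83.0% vs 79.0% (+4.0) |
| Related, 12 | 22.1% vs 23.8% (−1.7) | 33.8% vs 29.8% (+4.0) |
| Related, 20 | 14.0% vs 15.1% (−1.1) | 22.0% vs 19.1% (+2.9) |

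Differences are in percentage points, from unrounded values. On the main-study clock with no gap, the crude figure is 1.0 to 2.9 points too low.

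**6. Sensitivity.** For any TEAE on the extension clock with d = 0.15, having all leavers go at week 12 or at week 1 instead widens the shortfall to as much as 12.2 points. Over d = 5% to 30% and all three leaving patterns it runs from 1.4 to 24.5 points.

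**The case against.** The strongest reply is that the study is descriptive. SAP 4.1 disclaims hypotheses, thresholds and comparators, and the share of treated subjects with a TEAE is a legitimate proportion. No passage calls it a one-year risk. The plan also gives events per subject and event frequency, lists early terminations and AEs (listings 16.4 and 16.11), and says analyses are done at each efficacy assessment, which might yield results by visit. On the SAP 4.2 clock, completers differ by only 28 days. The 15% in Protocol 10.3.7 is attached to the number enrolled, so it may mean subjects who do not roll over rather than loss during the extension. For scale, an exact 95% interval around 72/161 runs from 36.9% to 52.7%, wider than the 4-point shifts above.

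Most of this stands, and it limits the point. The crude table should stay, and 15% in-study dropout is an assumption. The reply does not supply a time or injection denominator. The 14.3 table titles show no by-visit TEAE results, and counts per subject do not correct for subjects seen for less time. An interval that reflects sampling error alone also does not cover a shift caused by follow-up.

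A reader might infer that the percentage understates one-year risk. The documents do not support that as a general statement: once the entry gap is counted, many subjects are observed beyond 52 weeks and the error can reverse. Nor is observation time widely spread on every reading; among completers that holds only on the main-study clock.

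**Conclusion.** The point holds in a limited form. Followed as written, the plan yields a primary estimate tied neither to 52 weeks nor to five injections, over a window that the documents define in conflicting ways. What follows from the documents alone is the missing exposure summary, the conflicting windows, and the ceiling of four Ampion injections for former saline subjects. The size is illustrative. With 15% uniform dropout it is about 1 to 4.5 points too low against 40-week risk on the extension clock, and about 2 to 4 points too high against 52-week risk on the main-study clock with the gap counted. These figures rest on a constant hazard (including through the untreated gap), on pooled all-grade rates from Table 1.5.4 with an assumed follow-up, and on assumed leaving and gap patterns. Since the sign changes with the clock, no direction of bias should be claimed until the window is fixed. The crude percentage is not invalid. It answers a narrower question than the objective. This is a cheap improvement, not a defect that undermines the study.

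**What to change.** 1. Define one time origin and one observation window for TEAEs, and reconcile Protocol 9.3 and 10.3.6 with SAP 4.2, 4.7.4 and 5.2, including the 12-week and end-of-study statements on AE follow-up. This comes first, because the analyses below cannot be specified without it.
2. Keep the crude percentage with its exact interval.
3. Add to SAP 4.1 and the Section 7 table list:
   - (a) an exposure table giving patient-years and Ampion injections received, with first-event and total-event rates per 100 patient-years and confidence intervals;
   - (b) Kaplan-Meier cumulative incidence of first TEAE at Week 40 of the extension, and also at 52 weeks if the main-study clock is chosen;
   - (c) TEAEs by number of Ampion injections received, with events in the untreated gap shown separately.

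Injection, visit and AE dates are already collected, so no new data are needed. The cost is a few extra tables and their programming.

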When the clinical trials of Ampion were designed, it was assumed that the vehicle for the product, saline, would have little to no effect in reducing pain, stiffness, or improving physical function. This control was determined not to be a true placebo, but rather turned out to be active treatment. To address this, Ampio proposed a 12-week Main Study (AP-003-C) with a 6:1 randomization to protect the blind and prevent any potential bias associated with an open label assessment. In follow up to the Main Study, Ampio is adding a 40-week add-on, open label study to address the safety of repeat injections for a year. The Open Label Study will also analyze efficacy using the Western Ontario and McMaster Universities Arthritis Index (WOMAC®) osteoarthritis Index 3.1, and the Patient's Global Assessment of disease severity (PGA). This study will analyze response according to these individual criteria as well as responder analysis of OMERACT-OARSI criteria.

The Osteoarthritis Research Society International (OARSI) and Standing Committee for Clinical Trials Response Criteria Initiative Outcome Measures in Rheumatology (OMERACT) committee, in concert with the international rheumatology community, worked to develop a uniform core set of outcome measures for osteoarthritis. While the committee initially developed two sets of responder criteria to present the results of changes after treatment in three symptomatic domains (pain, function, and patient's global assessment) as a single variable for clinical trials, the committee ultimately worked to create a simplified set of responder criteria, Scenario D, which captured the criteria for response.

In the original plan, for each domain, a response was defined by both a relative and an absolute change, with different cut-offs with regard to the drug, the route of administration and the OA localization. The formal OMERACT-OARSI scenarios defined a responder as:

- a. having achieved a high degree of improvement in pain or a moderate degree of improvement in 2 of the 3 response domains (pain, function, global assessment) (scenario A)

OR

- b. as having achieved a high degree of improvement in either pain or function, or a moderate degree of improvement in 2 of the 3 response domains (scenario B)

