All efficacy variables will be assessed at Visit 9 (Day 0), Visit 11 (Day 84 ± 14), Visit 13 (Day 168 ± 14), Visit 15 (Day 252 ± 14), and Visit 17 (Day 280 ± 14). Except where noted to be otherwise, all statistical tests will be two-sided and will be at the 5% level of significance.

Unless otherwise specified, continuous variables will be summarized with the number of non-missing observations, mean, standard deviation, median, minimum, and maximum displayed. Categorical data will be summarized as counts and percentages. All efficacy assessments will be summarized as the measured value and as the change from baseline by treatment at each time point. Summary statistics will include number of observations, mean, standard deviation, median, minimum and maximum. Change from baseline will also include a 95% confidence interval.

Except where otherwise specified, missing data will not be estimated or carried forward in any of the descriptive analyses. No multiple comparison adjustment will be made for the secondary efficacy analyses. Data transformation or use of rank-based tests may be used if endpoints depart substantially from a normal distribution.

Baseline (Day 0 of AP-003-C main study) is defined as the last pre-treatment assessment. Because the secondary analyses are considered supportive to the primary analysis (i.e., not required to demonstrate efficacy of the test article), there is no requirement under ICH to adjust for multiplicity

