- Change in contralateral knee pain (WOMAC A) between Visit 9 and Visit 17
- Change in contralateral knee stiffness (WOMAC B) between Visit 9 and Visit 17
- Change in contralateral knee function (WOMAC C) between Visit 9 and Visit 17
- Time to Total Knee Replacement (TKR)
- Use of rescue analgesia (amount of acetaminophen used)

Exploratory efficacy analyses include the mean change and percent change in WOMAC A, WOMAC B, WOMAC C, WOMAC A1-2, WOMAC A3-5, PGA and amount of acetaminophen used from Visit 1 to Visit 17 using an analysis of covariance model, adjusted for baseline value.

Percent responders using the OMERACT-OARSI responder criteria will be analyzed defined as the percent of subjects whom respond to treatment from Visit 1 to Visit 17. Interim visits will also be analyzed.

1. High improvement in pain or in function $\geq 50\%$ and absolute change in Likert pain scale of ≥ 1 OR
2. Improvement in at least two of the 3 following:
 - a. pain $\geq 20\%$ and absolute change in Likert score ≥ 0.5
 - b. function $\geq 20\%$ and absolute change in Likert score ≥ 0.5
 - c. subject's global assessment $\geq 20\%$ and absolute change in Likert score ≥ 0.5

All of the above endpoints will be evaluated via descriptive statistics and confidence intervals.

The WOMAC Pain Score, the WOMAC Function Score, then PGA score and the OMERACT-OARSI responder criteria, will be analyzed via a repeated measures analysis of variance to determine if there is a significant time effect for these endpoints. Also, to aid in the interpretation of these results, a stability analysis will be performed on these same endpoints. That is, mean pairwise differences between administration time points will be calculated along with their 95% confidence intervals. If stability is achieved at some time point, then the following mean differences should be not be different from zero, in that the confidence interval should include zero.

Adverse events will be tabulated for both number of subjects and number of events by subject and overall study population, summarized by any event, body system, and preferred term. Summaries by serious, severity, and relationship will also be done.

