2.4 Sample Size

The original AP-003-C study used total of 170 subjects (140 Ampion; 25 Saline) to test the following hypotheses.

$$H_0: \pi \leq 30\% \text{ versus } H_A: \pi > 30\%$$

This study is observational, using subjects who consent from the AP-003-C study, so no formal sample size was calculated. In following ICH E1A safety guidelines to assess clinical safety in long-term treatment of non-life-threatening conditions, it is anticipated that 100 subjects will be enrolled into this study.

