This is an Open Label Extension study, which is designed to assess the safety of patients who have previously completed the main AP-003-C study. It is also desirable to assess the efficacy of all patients relative to their original baseline and first injection and exposure to the investigational product. Thus, the previously mentioned statistics will be calculated using the baseline from the main study, AP-003-C.

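### SAP 4.1 dates every subject's first Ampion exposure to the main-study baseline, but about one in seven main-study subjects received saline then; results from that baseline should be shown by main-study arm

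*SAP*

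**What the plan says.** SAP 4.1 lists the responder rates and the mean and percent changes, then adds that it is desirable to "assess the efficacy of all patients relative to their original baseline and first injection and exposure to the investigational product". It concludes: "Thus, the previously mentioned statistics will be calculated using the baseline from the main study, AP-003-C". Visit 9 is among the efficacy assessments: "All analyses will be descriptive in nature and will be performed at each efficacy assessment (Visit 9 (Enrollment), Visit 11 (Week 12" and later visits.

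The main study had a saline arm. Protocol 1.2 states that "Ampio proposed a 12-week Main Study (AP-003-C) with a 6:1 randomization to protect the blind", and SAP 2.4 gives its size as "140 Ampion; 25 Saline". Protocol 3.1 offers the extension to all main-study completers, with no restriction by arm. Protocol 5.1.1 places the Visit 9 WOMAC and PGA before the Visit 9 injection. Protocol 5 gives extension injections at Visits 9, 11, 13 and 15.

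On reporting, Protocol 10.3.11.5 defines baseline as Day 0 of the main study and adds: "Change from baseline will also include a 95% confidence interval". Protocol 10.4.2 describes the OMERACT-OARSI rate as "defined as the percent of subjects whom respond to treatment from Visit 1 to Visit 17". SAP section 7 presents every table by treatment arm, but no arm is defined for this single-treatment study.

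**The concern.** The SAP sentence is untrue for an identifiable group. A subject randomised to saline in AP-003-C had no Ampion at the main-study baseline. When that subject is assessed at Visit 9, the whole change from the main-study baseline reflects saline, time and background improvement. The plan nevertheless puts it into a summary described as efficacy since first exposure to the investigational product.

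The exposure count is also wrong after Visit 9. The objective refers to five Ampion injections in total; former saline subjects can reach at most four.

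A second, separate issue concerns all subjects. Protocol 1.2 says of saline that "This control was determined not to be a true placebo, but rather turned out to be active treatment". If saline improves scores, an uncontrolled change from the main-study baseline cannot show that Ampion adds anything. What is at stake is the labelling and interpretation of the exploratory efficacy results.

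**Working it through.** **Inputs**
- Saline share of the main study: 1/7 = 14.3% (6:1, Protocol 1.2); 25/165 = 15.2% or 25/170 = 14.7% (SAP 2.4, where the two arms sum to 165 but the stated total is 170).
- KL 4 pain change, combined single-injection studies (Protocol Table 1.5.2): saline -0.62, SD 0.883, N 223; Ampion -0.82, SD 0.817, N 194; unadjusted difference -0.21, p = 0.0125.
- Extension size: up to 161 (Protocol 4.1), 136 (Protocol 10.3.7) or 100 (SAP 2.4).

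**Step 1. Reproduce the plan's figure.** Pooled SD = sqrt[(222 × 0.883² + 193 × 0.817²)/415] = 0.853. SE = 0.853 × sqrt(1/223 + 1/194) = 0.0837. With the stated difference, t = 0.21/0.0837 = 2.51 and p = 0.0125, as printed. (The rounded means differ by 0.20; the stated 0.21 is consistent with rounding.)

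**Step 2. Ampion injections received before each assessment**

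| Visit | Ampion in main study | Saline in main study |
|---|---|---|
| 9 | 1 | 0 |
| 11 | 2 | 1 |
| 13 | 3 | 2 |
| 15 | 4 | 3 |
| 17 | 5 | 4 |

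Only at Visit 9 is the former saline subjects' change free of any Ampion effect. Afterwards it is mixed.

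**Step 3. Effect of pooling on the Visit 9 mean.** Assume roll-over in proportion to allocation and full persistence of the Week 12 change.
- Pooled mean = w × (-0.62) + (1 - w) × (-0.82).
- w = 1/7: -0.79. w = 25/165: -0.79.
- Roll-over by arm is not given. For w from 5% to 25% the mean runs from -0.81 to -0.77, against -0.82 for Ampion-first subjects alone.
- Visit 9 may fall up to 170 days after Visit 7. If only half of each change persisted (-0.31 and -0.41), the pooled mean at w = 1/7 would be -0.396, a shift of 0.014.

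**Step 4. What the one-sample interval can show.** Suppose Ampion equals saline: mean -0.62, SD 0.883, interval = mean ± t(0.975, n-1) × SD/√n.

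| Planned N | All subjects | Former saline subjects removed |
|---|---|---|
| 161 | -0.757 to -0.483 | -0.769 to -0.471 (n = 138) |
| 136 | -0.770 to -0.470 | -0.782 to -0.458 (n = 117) |
| 100 | -0.795 to -0.445 | -0.809 to -0.431 (n = 86) |

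With the smallest single-study saline mean (AP-003-A: -0.51, SD 0.906), the interval at N = 161 is -0.651 to -0.369.

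If half the saline change persisted, it would be -0.31 ± 0.137, or -0.447 to -0.173, at N = 161. At one quarter (-0.155) it would just exclude zero at N = 161 (-0.292 to -0.018) and include it at N = 100 (-0.155 ± 0.175, or -0.330 to 0.020).

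**Step 5. Is the saline-first share the cause?** Let only those subjects improve (w = 1/7, mean -0.62) and the rest have mean zero (SD 0.817). The pooled mean is 0.143 × (-0.62) = -0.089, and the interval at N = 161 is -0.222 to 0.044, which includes zero. So the exclusion of zero in Step 4 comes from the lack of a control, not from the former saline subjects.

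**The case against.** The strongest reply is that this is a descriptive summary in a single-arm safety extension. SAP 4.1 says openly that there is no comparator and no hypothesis test. The protocol's check against zero (10.3.5 and 10.4.2) concerns differences between successive administrations, not change from the main-study baseline. That stands: no false-positive test is built into the plan.

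It can also be said that other baselines are available. Protocol 10.3.6 foresees several, the Protocol 10.4.2 endpoint list measures responder status from Visit 9, and SAP 4.2 sets Day 0 at the first dose of this study. SAP 4.1 can be read as adding the main-study baseline to these. This is fair, but none of them is tied to main-study arm, and the SAP 4.1 sentence remains wrong for former saline subjects.

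Finally, SAP section 7 (tables by arm), SAP 5.2 (study drug defined as either Ampion or saline) and the planned randomisation listing could mean that a split by main-study arm is intended. They could equally be carried over from the main-study SAP. The text is ambiguous, which is a reason to define the arm.

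A reader might infer that saline response inflates the Ampion result. Table 1.5.2 points the other way: saline subjects improved less, so including them dilutes it. Nor does it help to set their contribution of 0.089 to a pooled mean against the adjusted between-arm difference of 0.19; these are different quantities.

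**Conclusion.** The SAP 4.1 statement is wrong as written for about 14-15% of main-study subjects and should be corrected. Pooling them gives the wrong estimate for the stated exposure at every visit, and at Visit 9 their part of it contains no Ampion effect. The numerical consequence for the Visit 9 mean is small: about 0.03 points of dilution, or 0.01 to 0.05 for a saline-first share of 5-25%. This assumes that the earlier 12-week KL 4 changes carry over to this study and persist to Visit 9. The documents give no figures for sizing the effect at later visits.

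The limit on interpretation is the larger matter and does not depend on the former saline subjects. At the planned sizes an interval from the main-study baseline would exclude zero even if Ampion equalled saline, unless most of the Week 12 change had been lost.

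It is tempting to join the two and say that the interval excludes zero because some subjects had saline. Step 5 shows that this does not follow. Because efficacy is exploratory and nothing is tested against zero, this is a correction the plan should make, not a threat to the primary safety objective.

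**What to change.** Amend the SAP as follows.

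1. In 4.1, define the first-exposure baseline as the main-study baseline for subjects randomised to Ampion in AP-003-C, and as Visit 9 for those randomised to saline.
2. In section 7, define treatment arm as main-study arm. Show change and responder rates from the main-study baseline in separate Ampion-then-Ampion and saline-then-Ampion columns at every visit, with no pooled figure labelled as Ampion efficacy.
3. In 4.1, state that a one-sample interval or responder rate from the main-study baseline, including the Protocol 10.4.2 rate, is descriptive and is not evidence of an Ampion effect over saline.

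An Ampion-minus-saline difference at Visit 9 is optional. It would be restricted to subjects who chose to roll over, after a variable delay, and would be imprecise: the half-width is 1.96 × sqrt(0.883²/23 + 0.817²/138) = 0.39 at N = 161, and 0.49 at N = 100.

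The cost is SAP wording and one column per efficacy table. It needs the main-study allocation, which the sponsor should already hold, and no new data. The Ampion-first column has about 14% fewer subjects (138 of 161, or 86 of 100). The saline-first column is small: with mean -0.62 and SD 0.883, its Visit 9 interval would run from -1.002 to -0.238 at n = 23 and from -1.13 to -0.11 at n = 14.
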